Our preliminary studies showed that acute autonomic blockade improved insulin resistance (Figure 3). In those studies, we used an acute dose of the ganglionic blocker trimethaphan, and a dose of insulin that suppresses endogenous glucose production (EGP) so we could selectively measure insulin resistance to glucose uptake. Animal studies suggest that sympathetic tone plays an even a greater role in regulating EGP by the liver (2). However, to our knowledge the magnitude of this effect in humans, and in particular in obesity hypertension, has not been assessed. Therefore, we now propose to determine the role of the autonomic nervous system in insulin resistance at baseline, and after central sympathetic inhibition with moxonidine vs. treatment with amlodipine (Figure 6). Subjects will be studied at baseline and during treatment using a two-step hyperinsulinemic euglycemic clamp (Figure 7): first using a low dose insulin infusion, coupled with stable isotopes (glucose tracer) to assess insulin sensitivity of suppression of endogenous glucose production (EGP, Specific Aim 1a), followed by a higher dose of insulin that suppresses EGP, to electively assess glucose uptake (Specific Aim 1b).

Specific aim 2. To test the hypothesis that sympathetic activation contributes to impaired vasodilation in obesity hypertension.

There is significant evidence that obese hypertensive subjects have impaired NO-mediated dilation, and our group confirmed this abnormality in resistance vessels (brachial artery dilation to acetylcholine). In addition, we showed that autonomic

blockade reverses this impairment, indicating that a significant component of impaired NO-dilation is secondary to sympathetic activation, at least in initial stages of obesity hypertension (3). Considering that insulin vasodilation is NO-mediated, sympathetic blockade may improve this mechanism blunted in insulin resistant states. Current evidence suggests that the ability of insulin to increase the number of perfused capillaries (microvascular recruitment) is important for stimulating glucose uptake, by enhancing its delivery to muscle cells (4-6). Therefore, insulin ability to stimulate microvascular recruitment, via NO-mediated dilation, is an important component of insulin sensitivity of glucose uptake (7).

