6.0 Study Procedures / Study timeline

As explained before, we propose a double-blind, randomized, 9-week, parallel group study. The clinical trial will consist of 9 visits.

Visit 1 (Screening and clinical characterization): We will enroll obese hypertensive subjects off medications. Antihypertensives and medications that can affect autonomic function will be stopped at least for 5 half-lives (~2-3 weeks). They will be asked to monitor their blood pressure at home and will be provided with blood pressure monitors if necessary. Patients with pre-

hypertension are included if they have insulin resistance and sympathetic activation. Stage II hypertension is excluded because of the likelihood that more than one antihypertensive is needed to control BP.

[figure not shown]
Visit 2 and 3 (Baseline measurements): After 3 weeks off medications (or at least 5 half-lives), if the patients still meet the inclusion/exclusion criteria, we will perform the following baseline measurements the day before performing the first hyperinsulinemic-euglycemic clamp:

- Sympathetic activity (MSNA) (visit 2 only)
 - We may perform some autonomic nervous system function tests during MSNA such as Valsalva maneuvers
- Heart rate
- Blood pressure (supine and 1, 3, 5, 15, 30 minutes standing)
- Blood samples collected in supine position and after 30 minutes of standing for catecholamines, renin activity, angiotensin II and aldosterone levels) (visit 2 only)
- Blood for FAC analysis of immune cells (visit 2 only)
- Flow mediated dilation and 24-hr blood pressure (visit 2 only)
- FAC analysis of harvested endothelial cells (visit 2 only)
- Non-invasive determination of arterial stiffness using tonometric (Sphygmocor) method (visit 2 only)
- Hyperinsulinemic clamp (visit 3 only)
- Body impedance (visit 2 or 3)
- Blood volume measurement (visit 2 only)
- DEXA scan (visit 2 only)

Visit 4-7 (Randomization): Randomization, blood pressure adjustments and monitoring will be held from visit 4 to visit 7. Patients will be randomized with a permuted block double-blinded scheme. Moxonidine and amlodipine will be started at 0.2mg bid and 5mg, respectively. Blood pressure will be measured using the Sprint protocol with home monitors provided by us, and at weekly visits. A blinded study physician will increase medication dose once if needed. The dose titration period can be extended if necessary, to reach a stable BP.

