Visit 8-9: We will repeat the baseline measurements mentioned above after 9 weeks of treatment during these visits. Hyperinsulinemic-euglycemic clamp will be performed in visit 9 (treatment). No DEXA scan will be performed at visit 8.

Study procedures during the hyperinsulinemic-euglycemic clamps:

- 1. We will draw a blood sample to measure baseline levels of [6,6-2H2]-dideuterated glucose. We will then start the continuous infusion of [6,6-2H2]-dideuterated glucose. After at least 90 minutes, we will do baseline measurements of HP and BP. We will take blood samples every 15 minutes for 30 minutes (3 total) to measure plasma glucose, insulin, glucagon, C-peptide, and [6,6-2H2]-dideuterated glucose.
- 2. We will then perform a two-hour glucose clamp. In ancillary studies ([name], unpublished) new found that an autonomic blockade enhances insulin suppression of EGP, we decided to use the lower dose of 15 mU/m²/min insulin produced a >50% suppression of EGP (Bock et al. 2007). Plasma glucose will be monitored every 5 minutes and euglycemia (90-100 mg/dl) will be maintained with variable infusion of 20% glucose. Potassium chloride 10 mmol/hr will be infused to prevent hypokalemia.
- 3. Once the glucose clamp is started, the glucose tracer infusion will be gradually reduced to 1.0 mg/m2 (half the starting dose), to account for the expected decrease in hepatic glucose output. To minimize changes in glucose isotopic enrichment, tracer will be added to the 20% Dextrose solution. We will alter tracer delivery commensurate with changes in glucose flux to maintain a constant plasma specific activity of glucose, as done previously (28-31).
- 4. Within the last 30 minutes after achieving stable glucose levels, samples will be drawn for every 15 minutes for 30 minutes (3 total) to measure glucose and [6,6- 2 H2]-glucose levels. At the third blood draw, we will also obtain samples for insulin, glucagon, C-peptide, catecholamines, and free fatty acids. In particular, glucagon and free fatty acids regulate EGP, but we have previously shown that their suppression during hyperinsulinemia is not altered by sympathetic withdrawal (32).

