- 5. We will then increase the dose of insulin to 60 mU/m2 /min for an additional two hours. At this dose, insulin produces complete suppression of hepatic glucose production even in insulin resistant patients. Glucose utilization under these conditions, therefore, will reflect glucose uptake. The glucose infusion rate during the last 30 minutes of the clamp will be used as a measure of insulin sensitivity of glucose uptake. Within the last

30 minutes after achieving stable glucose levels, samples will be drawn every 15 minutes for 30 minutes (3 total) to measure glucose and [6,6-2H2]-dideuterated glucose levels. At the third blood draw, we will also obtain samples for insulin glucagon, C-peptide, catecholamines, and free fatty acids.

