a) Specific Aim 1a - The null hypothesis is that there will be no changes in the insulin-mediated suppression of endogenous glucose production in response to sympathetic blockade with MOX. We will evaluate this hypothesis at Visit 9 (post treatment) by measuring EGP at baseline (EGPBsI) and during the last 30 minutes of a hyperinsulinemic euglycemic clamp (EGPClamp) in a double-blind randomized trial (protocol shown in figure 6). For each study arm, the primary endpoint will be DEGP = (EGPBsI – EGPClamp) the difference in the change of insulin-mediated suppression of basal EGP between the pre and post treatment visit. The primary analysis will be performed between the moxonidine and amlodipine arms, at Visit 9 using Welch's unequal-variance an unpaired t-test to test whether the primary end point will be equal in these two treatment groups. Note that although we are collecting multiple measures over time, this endpoint is based on a single visit and a scalar response feature ΔEGP. Hence, a fixed effects analysis is appropriate for this aim. Appropriate non-parametric analysis methods will also be used if data are not normally distributed. Since the degree

of obesity, baseline sympathetic activity, blood pressure, age and gender may affect EGP, these variables could confound the effect of treatment on the change in EGP. For this reason, in a secondary linear regression analysis we will compare DEGP in the moxonidine and amlodipine arms adjusted for these variables. We will also assess the effects of treatment on EGP over time by conducting a repeated-measures GEE regression analysis of EGP against treatment and these confounding variables at baseline and the 9 subsequent visit times. These analyses will use a normal random component and the identity link function. Spaghetti graphs and residual analyses will be used to assess the model fit. Restricted cubic splines will be used if needed to account for non-linear effects of time on treatment response (33).

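### The secondary GEE of EGP is written for baseline plus nine later visits, but EGP is measured at only two visits

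*Combined protocol and SAP*

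**What the plan says.** Section 10.0, under Specific Aim 1a, makes a Welch t-test the primary analysis and a covariate-adjusted linear regression a secondary one. It then adds a second secondary analysis, a repeated-measures GEE with normal errors and identity link. This is meant to show how treatment affects EGP over time. EGP is regressed on treatment and the listed confounders "at baseline and the 9 subsequent visit times". Restricted cubic splines are available if the response to treatment is not linear in time.

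Section 6.0 describes what will be collected:

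- "The clinical trial will consist of 9 visits", and this count includes screening.
- In the list of baseline measurements for Visits 2 and 3: "Hyperinsulinemic clamp (visit 3 only".
- Visits 4 to 7 are for randomisation, dose adjustment and blood pressure monitoring. No clamp is listed there.
- For the end of treatment: "Hyperinsulinemic-euglycemic clamp will be performed in visit 9 (treatment".

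Section 2.0 agrees: "Subjects will be studied at baseline and during treatment using a two-step hyperinsulinemic euglycemic clamp".

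**The concern.** EGP comes from the glucose tracer infused around the clamp, so a visit without a clamp has no EGP value. The analysis section describes ten occasions and the procedures section supplies two. Whoever writes the analysis program cannot follow the text and will have to decide, possibly after seeing data, which time points to use, which EGP quantity is the outcome (basal, clamped or their difference), how treatment is coded before treatment has begun, and whether its effect may differ by visit. The last two choices can change what the treatment coefficient means. A pre-specified secondary analysis should not leave that open.

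**Working it through.** **1. Count the occasions.** The GEE text gives 1 + 9 = 10. Section 6.0 gives 9 visits in all. After the baseline clamp at Visit 3, only Visits 4 to 9 remain, which is 6. Nine later visits cannot exist on the plan's own schedule, whatever is measured at them. Visits with a clamp: Visit 3 and Visit 9, so 2.

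**2. Can a spline in time be fitted across two visits?** A three-knot restricted cubic spline has a linear and one non-linear column. Compare the number of columns with the rank of the design matrix:

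| Model | Columns | Rank, 2 times | Rank, 10 times |
|---|---|---|---|
| Intercept + spline + arm | 4 | 3 | 4 |
| Intercept + spline + arm + spline × arm | 6 | 4 | 6 |
| Intercept + visit + arm + visit × arm | 4 | 4 | (not needed) |

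With two times the spline models are not identified. The model with arm, visit and their interaction is saturated and estimable.

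**3. Could the ten be blood draws within one clamp?** Section 6.0 starts with a draw before the tracer ("We will draw a blood sample to measure baseline levels of [6,6-2H2]-dideuterated glucose"). It then takes three basal samples ("We will take blood samples every 15 minutes for 30 minutes (3 total"), three at the lower insulin dose and three at the higher: 1 + 3 + 3 + 3 = 10. The total matches, but the reading does not fit well. The text says visit times. The pre-tracer draw cannot by itself yield an EGP value, which leaves 10 − 1 = 9 tracer samples per clamp, and 2 × 9 = 18 over both clamps. Three of the nine fall at the dose where, according to Section 6.0, "insulin produces complete suppression of hepatic glucose production even in insulin resistant patients".

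**4. What would the treatment coefficient estimate? (conditional)** Let D3 and D9 be the arm differences in the chosen EGP outcome at Visits 3 and 9. Assume complete pairs and leave the other covariates aside.

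- Randomised arm as a main effect over both visits, no interaction: coefficient = (D3 + D9)/2. Randomisation gives D3 an expected value of 0, so the expected coefficient is half the expected D9.
- With a treatment-by-visit term: interaction = D9 − D3, and the Visit 9 contrast (arm plus interaction) = D9. Both have the expected value of D9.

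For scale only, D3 = 0 and D9 = 3 give (0 + 3)/2 = 1.5 without the interaction and 3 with it. The 3 µmol/min/kg is borrowed from the Aim 1a sample size, where it is a difference in inhibition of EGP. The GEE sentence names EGP itself, for which the documents give no expected effect.

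**5. What depends on the GEE?** Section 10.0 gives it no sample size or power, so there is no such figure to reproduce. The 29 per group belongs to the primary t-test. With a difference of 3, SD 4.0 and two-sided 0.05 (sidedness assumed), the t-test power at 29 per group is 80.1%, matching the stated 80%. Nothing above changes that calculation.

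**The case against.** Four points can be made for the plan.

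- *The mean model can be fitted.* EGP on treatment and confounders runs on two visits, and the splines apply only if needed. This stands. A reader might infer that no GEE of EGP is possible, and the documents do not support that. What fails is the ten-occasion description and any spline across visits.
- *An interaction may be intended.* The stated purpose, and the remark about time modifying the response, both point to a treatment effect that varies with time. This also stands. A reader might infer that the plan will report half the true effect, but that needs a coding that the plan does not state and that fits its stated purpose least well. Coding treatment as received, or ANCOVA on the Visit 3 value, would also avoid the dilution.
- *Visit times may be a slip for sampling times.* This is possible. EGP can be calculated at the higher insulin dose, and a value near zero is still an outcome. The pre-tracer draw and the word visit count against it. If it was meant, the sentence still has to say so.
- *Other regressions cover the question.* Section 10.0 already plans covariate-adjusted comparisons of the arms, so little rests on the GEE. This supports a low priority. It does not make the GEE redundant: with the 20% drop-out planned for, a GEE can use a subject with one clamp, whereas a regression of visit differences cannot.

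The visit count itself has no good answer. The study-scheme figure is not reproduced in the text available, but Sections 2.0 and 6.0 are explicit without it.

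**Conclusion.** The point holds as a low-priority correction to a secondary analysis. The plan describes 10 occasions, the schedule has 9 visits, and EGP is available at 2. The analysis cannot be carried out as described, and non-linear time effects across visits cannot be estimated. These conclusions rest only on the visit schedule and on EGP requiring the tracer clamp.

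The possible dilution to one half is a conditional note. It assumes that arm is coded at both visits, that Visit 3 values are outcomes, that there is no interaction and that pairs are complete. It should not be read as a predicted bias in this trial. Nor does the point reach the primary Welch test, its sample size or its power.

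**What to change.** Reconcile the GEE sentence in Section 10.0 with the visit and sampling schedule in Section 6.0. First establish whether within-clamp time points were meant. If so, say so, list the samples that yield EGP, and state how the two clamps enter the model. Otherwise:

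- restate the GEE for Visits 3 and 9, with visit as a categorical term and a treatment-by-visit term;
- name the outcome: basal EGP, clamped EGP at a stated insulin dose, or the difference between basal and clamped EGP;
- state how treatment is coded at Visit 3, and report the Visit 9 treatment contrast;
- remove the nine later visit times and the splines across visits.

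The cost is SAP wording only. No visits, samples or subjects are added.

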10.0 Statistical Considerations

In this proposal, we will be testing the general hypothesis that nine weeks of treatment with the sympathetic blocker, moxonidine, will improve insulin sensitivity (Specific aim 1), microvascular blood flow (Specific aim 2), and inflammation (Specific aim 3), in obese hypertensive human subjects. We will be comparing the changes before and after treatment with the central sympathetic inhibitor moxonidine (MOX), versus the changes produced with treatment with the calcium channel blocker amlodipine (AML), an antihypertensive medication considered to have neutral metabolic and anti-inflammatory effects. Our main scientific goal is to demonstrate the efficacy of MOX in a superiority trial, and for that reason the study is powered to perform the main statistical analysis between the MOX and AML arms. The clinical comparison between the two responses, not previously done, will provide important new information. Nonetheless, as a secondary analysis, the differences in primary outcomes between the treatment and baseline study days will be compared across the two study arms using a linear regression model. Given the fact that the degree of obesity, baseline sympathetic activity and blood pressure may affect EGP these variables as well as gender and age will be included as covariates in the model to take into account potential confounding effects. We make no a priori assumptions about the outcome of these studies. Any result, therefore will provide important new information.

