Sample size calculation. Power calculations are based on previous studies comparing the suppression of EGP between subjects with impaired fasting glucose and normal fasting glucose (34). In this study among obese subjects with impaired fasting glucose (N=30), the mean and the standard error of mean (SEM) for EGP at baseline was 15.2 \pm 0.2 μ mol×min-1 \times kg-1, and during the clamp, EGP was $10.2\pm0.7~\mu\text{mol}\times\text{min-1}~\times~\text{kg1}$. Hence, the standard deviation (SD) of EGP at baseline and during clamp was $0.2\sqrt{30} = 1.1$ and $0.7\sqrt{30} = 3.8$, respectively. We will power our study to detect a difference in inhibition of 3 µmol×min-1 ×kq-1. Making the conservative assumption that clamped and baseline EGP values are independent, we estimate the SD of this difference to be *(1.1, +3.8) = 4.0. With this SD, 29 subjects per group would provide 80% power to detect a mean difference in the inhibitions of 3 μ mol \times min-1 \times kg-1 with the type I error of a = 0.05. Assuming a drop-out rate of 20%, which includes the subjects that will be enrolled based on HOMA but later shown not to have insulin resistance during the clamps (see Section C.2), we will need to enroll 36 subjects in each study arm. This sample size will also be used in Aims 1b, 2 and 3 even though smaller sample sizes would suffice for these aims.

Specific Aim 1b - The null hypothesis is that chronic sympathetic blockade will not improve whole body insulin sensitivity. We will measure insulin sensitivity as the glucose infusion rate, corrected by body weight (MBW) needed to maintain euglycemia during the last 30 minutes of a hyperinsulinemic euglycemic clamp. The same three groups of subjects will be studied twice, at the beginning (BSL) and the end of 9 weeks of treatment with either the sympathetic blocker moxonidine (MOX) or the calcium channel blocker amlodipine (AML). The null hypothesis is that we will not see any difference in the change in body-weight-corrected insulin sensitivity with MOX as compared with AML. The primary analysis will assess changes in MBW (MBW_clamp – MBW_bsl) between patients receiving MOX and will use a t-test similar to that described for Aim 1a.

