Sample size calculation. We estimated the sample size based on previous studies (17) using a similar design to the present study, which found a 21% improvement of insulin sensitivity with moxonidine. From our previous studies, we expect obese insulin resistant hypertensive subjects to have a MBW of 3.1 ± 0.99 mg/kg/min (17). An increase of 21% in the moxonidine arm will translate as a MBWMOX of 3.75 mg/kg/min (a difference of 0.65 mg/kg/min), after 9 weeks of treatment. Assuming that a SD of the difference of 0.75

mg/kg/min, a sample size of of 27 subjects per group will provide 88% power to detect this difference with a = 0.05.

Specific Aim 2 - The null hypothesis is that insulin will not produce any different changes in microvascular blood volume (MBV) using contrast enhance ultrasonography (CEU) in response to nine weeks of treatment with moxonidine as compared to amlodipine. We will measure MBV at baseline (MBVbsl), during the last 30 minutes of the lower insulin dose (15 mU/m2 /min) portion of the hyperinsulinemic euglycemic clamp (MBVegp), and during the last 30 minutes of the higher insulin dose (60 mU/m2/min) portion of the clamp (MBVclamp) on two different occasions (double blind, randomized, protocol shown in figure 6). Subjects will be randomized to treatment with moxonidine (MOX) or amlodipine (AML). The primary endpoint would be the average difference in the change in MBV (MBVclamp-MBVbsl) between the MOX and AML arms. The primary analysis will be conducted between the moxonidine and amlodipine arms using a t-test as described in Aim 1a.

Sample size calculation. We estimated the sample size based on our preliminary results (Figure 8) and previous studies in obese human subjects (35). In our study, on the SAL day, we expect to see a blunted increase in MBV only due to insulin among obese subjects (from 20.4 ± 3.6 to 18.8 ± 3.8 , as in the paper by Haenni and Lithell (17)). We believe that an increase of 3.5 arbitrary intensity units (AIU) of MVB (half of the what was seen in healthy subjects) during MOX treatment would be a clinically significant difference. Healthy subjects showed an increase from 18.7 ± 3.3 to 25.0 ± 4.1 in the same paper, and we have observed similar results (see figure 8). With a SD of 3.2 AIU, a sample size of 27 subjects per group would provide 97% power to detect a difference of 3.5 AIU with a = 0.05.

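### Aim 1b's primary t-test on the change in MBW does not adjust for the Visit 3 MBW the trial already collects; adjusting is a free improvement worth about 0 to 4 points of power in most plausible cases

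*Combined protocol and SAP*

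**What the plan says.** Section 6.0 schedules one clamp before treatment ("Hyperinsulinemic clamp (visit 3 only", in the baseline list) and one at the end ("Hyperinsulinemic-euglycemic clamp will be performed in visit 9 (treatment"). Section 10.0 confirms the pairing for Aim 1b: "The same three groups of subjects will be studied twice, at the beginning (BSL) and the end of 9 weeks of treatment". (There are only two arms.) Each subject who completes therefore has a pre-treatment and a week-9 MBW.

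The Aim 1b primary analysis concerns "changes in MBW (MBW_clamp – MBW_bsl) between patients receiving MOX and will use a t-test similar to that described for Aim 1a". The sentence names one arm only, but the null hypothesis just before it makes the comparison moxonidine against amlodipine. Section 10.0 uses BSL for the start of the study, so I read the formula as Visit 9 MBW minus Visit 3 MBW. The Aim 1a test that it points to is Welch's unpaired t-test, with non-parametric methods if the data are not normal.

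Adjustment appears only in a secondary linear regression: "degree of obesity, baseline sympathetic activity and blood pressure may affect EGP these variables as well as gender and age will be included". The Aim 1a text repeats that list. The baseline value of the outcome is not in it.

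For sizing, section 10.0 says "we expect obese insulin resistant hypertensive subjects to have a MBW of 3.1 ± 0.99 mg/kg/min", takes a difference of 0.65 mg/kg/min, and goes on: "Assuming that a SD of the difference of 0.75" mg/kg/min. It states 88% power at 27 per group. The number actually used comes from Aim 1a ("29 subjects per group would provide 80% power", 36 enrolled per arm) and is applied to every aim.

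**The concern.** A change score fixes the slope of week-9 MBW on baseline MBW at 1. When the true slope is lower, as it is when the two visits have similar spread and an imperfect correlation, the change score carries baseline noise that a regression would remove. Under randomisation both analyses estimate the same treatment difference, so the choice affects precision only. The plan already intends to adjust for five other variables in a secondary model, yet leaves out the one most likely to predict the outcome. What is at stake is modest: a somewhat wider interval and lower power than the same clamps could give.

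**Working it through.** Inputs, all from section 10.0: difference d = 0.65 (3.1 × 0.21 = 0.651); SD of the change 0.75; MBW 3.1 ± 0.99; alpha 0.05, taken as two-sided; 27 per group for the stated power; 29 evaluable per arm (36 × 0.8 = 28.8). Power is from the noncentral t with noncentrality d / (s × √(2/n)).

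**1. The plan's own figure.** With n = 27: 0.65 / (0.75 × √(2/27)) = 3.18 on 52 df, giving 87.8% against 88% stated. It reproduces. With n = 29: 0.65 / (0.75 × √(2/29)) = 3.30 on 56 df, giving 90.0%.

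**2. Adjusted analysis, reading 0.99 as an SD equal at both visits.**
- Implied correlation: r = 1 − 0.75² / (2 × 0.99²) = 1 − 0.5625/1.9602 = 0.713.
- Residual SD: 0.99 × √(1 − 0.713²) = 0.694.
- With n = 29: 0.65 / (0.694 × √(2/29)) = 3.57 on 55 df, giving 93.9%.
- Allowing for chance baseline imbalance (residual variance × (1 + 1/54)): 93.5%.
- A simulation of 40,000 trials gave 93.6% for the adjusted analysis and 90.3% for Welch's test on change. A separate simulation under no effect gave a type I error of 4.8-4.9% for the adjusted analysis.

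**3. Dropping the equal-SD assumption.** Keep the change SD at 0.75 and the Visit 3 SD at 0.99, and let the Visit 9 SD be s (assumed range). Then r = (0.99² + s² − 0.75²) / (2 × 0.99 × s), and the residual SD is s × √(1 − r²). The t-test stays at 90.0%.

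| Visit 9 SD | Residual SD | Adjusted power | With imbalance factor |
|---|---|---|---|
| 0.80 | 0.596 | 98.3% | 98.1% |
| 0.90 | 0.652 | 96.1% | 95.8% |
| 0.99 | 0.694 | 93.9% | 93.5% |
| 1.10 | 0.731 | 91.4% | 90.9% |
| 1.20 | 0.748 | 90.1% | 89.6% |
| 1.24 | 0.750 | 90.0% | 89.5% |

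The downside is bounded. The regression slope minimises the SD of (week 9 − b × baseline), and the change score is the case b = 1, so the adjusted residual SD cannot exceed 0.75. The worst case is s = √(0.99² + 0.75²) = 1.24, where the slope is 1. The loss there is one degree of freedom plus the imbalance factor: 89.5% against 90.0%.

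**4. If 0.99 is a standard error.** For an assumed 10, 20 or 30 subjects the SD is 0.99 × √10, √20 or √30, r is at least 0.97, and adjusted power is 90.4%, 90.2% or 90.1% before the imbalance factor. The gain is then practically nil.

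**5. Numbers per arm for 90%, under the step 2 assumptions.** The t-test needs 29. The adjusted analysis gives 90.0% at 25 without the imbalance factor, but 89.4% with it; 26 gives 90.6% with it.

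**6. If the change SD exceeds 0.75.** At 29 per arm the t-test falls below 80% once the change SD passes about 0.87. What adjustment then does depends on the cause.
- Lower correlation, both SDs 0.99 (assumed r): at r = 0.6 the change SD is 0.99 × √0.8 = 0.885, and power is 78.4% (t-test) against 86.0% (adjusted, imbalance included). At r = 0.5 the change SD is 0.99, and power is 69.0% against 80.2%.
- Larger Visit 9 spread, at an assumed change SD of 0.90: the t-test has 77.1%. The adjusted analysis (imbalance included) has 85.2% at a Visit 9 SD of 0.99, about 78% at 1.2 and 76.5% at 1.3.

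**The case against.** The planned analysis contains no error. Welch's test on change is valid, the 88% is right on its inputs, and Aim 1b has about 90% power at 29 per arm. The sample size is set by Aim 1a, so a smaller requirement for Aim 1b frees no subjects. The headline gain needs two things the plan does not state: that 0.99 is an SD (Aim 1a quotes standard errors) and that the Visit 9 SD equals it. The effect is expressed as a percentage increase; if the spread rose with the mean, the moxonidine Visit 9 SD would be about 0.99 × 1.21 = 1.20 and most of the gain would go. Replacing Welch's test with an ordinary regression would also drop the plan's allowance for unequal variances and its non-parametric fallback.

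All of this stands as a limit on the size of the gain and on the form of the fix. It does not turn the recommendation around, because the loss is at most about half a point while the gain can be 4 points or more.

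A reader might infer more than the documents support:
- *That Aim 1b is underpowered or its test wrong.* Step 1 shows otherwise.
- *That adjustment protects against any underestimate of the change SD.* Step 6 shows that it does so when the between-visit correlation is lower, and that the benefit vanishes when the cause is a larger Visit 9 spread.
- *That Aim 2 gains a known amount of precision.* The Aim 2 formula contains only the within-clamp change in MBV, which suggests a Visit 9 response. But MBV is measured on two occasions, the opening of section 10.0 speaks of changes before and after treatment, and the Aim 1a text that Aim 2 refers to speaks both of a single visit and of a pre-post difference. If Aim 2's endpoint is a pre-post difference, Visit 3 is already used. No figure can be claimed until this is settled.

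**Conclusion.** The point holds as a free improvement, not as a flaw. If 0.99 is an SD equal at both visits, adjusting for Visit 3 MBW takes Aim 1b from 90.0% to about 93.5-94% at 29 per arm, so the chance of missing a true 0.65 mg/kg/min difference falls from about 10% to about 6%. With the change SD fixed at 0.75, the gain is larger if the Visit 9 SD is below 0.99 and about 0-1 point if it is 1.1-1.24 or if 0.99 is a standard error. The worst case is 89.5%. These figures use an ordinary regression variance; the effect on power of the robust variance recommended below was not computed.

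**What to change.** Before unblinding, replace the Aim 1b primary-analysis sentence with one that prespecifies a linear regression of week-9 MBW on treatment (moxonidine against amlodipine) and Visit 3 clamp MBW. Use a heteroscedasticity-robust variance, to keep the plan's allowance for unequal variances. Keep Welch's t-test on the change, with the plan's non-parametric fallback, as a sensitivity analysis. State whether 0.99 is an SD or a standard error.

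For Aim 2, first state whether the endpoint is the Visit 9 insulin response or its pre-post difference. The same model can then be used: week-9 insulin-induced MBV change on treatment and the Visit 3 insulin-induced change. Do not use the week-9 pre-insulin MBV as a covariate, because it is measured after randomisation.

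The cost is a few sentences in section 10.0. Sample size, visits and measurements do not change.
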